9.3.2 Outcomes

9.3.2.1 Primary Outcomes

The primary outcome event for effectiveness is time to first COPD exacerbation after cohort entry. The event is defined as follows:

- Severe exacerbation:
 - Hospitalization with a principal discharge diagnosis of COPD and/or
 - An emergency department (ED) visit with a discharge diagnosis of COPD
 - An inpatient admission or an ER visit with a diagnosis code for acute respiratory failure in the primary position and a COPD diagnosis code in any position
- Moderate exacerbation:
 - \circ An antibiotic for a respiratory condition dispensed \pm an OCS

Time to the first COPD exacerbation will be measured from index date until the occurrence of a hospitalization for COPD (severe exacerbation) or ED visit for COPD (severe exacerbation) or prescription of an antibiotic \pm an OCS on the same day (moderate exacerbation). Severe and moderate exacerbations were considered as a composite for main analyses. Sensitivity analyses will include stratification by exacerbation severity.

Exacerbations will be categorized as moderate or severe and a count of any (severe or moderate), severe, and moderate will be provided.

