9.1 STUDY DESIGN

This is a non-interventional study with existing data. It will be a retrospective, observational, non-interventional, new user design, real world study of Commercial Insurance and Medicare beneficiaries, using administrative claims data for the period of 15th September 2016 through 31st March 2020.

Patients initiating Stiolto, or Trelegy will be identified using pharmacy claims database). The date of the first prescription claim (on or after 15th September 2017) will be defined as the index date. Patients will be required to have a diagnosis of COPD (ICD-9-CM: 491.xx, 492.xx, 496.xx; ICD-10-CM: J41-J44) on two separate medical claims. Patients 40 years or older will be included in the study. Patients will be required to have continuous enrolment for 12 months prior to the index date. Patients will be excluded if they show any

Proprietary confidential information © 2022 Boehringer Ingelheim International GmbH or one or more of its affiliated companies

use of COPD maintenance medications (ICS, LABA or LAMA in any combination), during the baseline period of six months pre-index date. This will satisfy the criteria for being considered as treatment naive. Patients with two separate medical claims with a diagnosis of asthma, lung cancer, interstitial lung disease, or cystic fibrosis during the study period will be excluded. Using propensity score matching (PSM) technique, we will develop matched cohorts of patients between Stiolto initiators and Trelegy initiators. We will conduct 1:1 matching using nearest neighbour matching approach with a caliper of 0.2. Exacerbation will be defined as a COPD hospitalization (severe exacerbation) or Emergency Department (ED) visit (severe exacerbation) with COPD, or use of approved respiratory antibiotics (e.g., Azithromycin) \pm Oral CorticoSteroids (OCS) medications within \pm 7 days of the office/outpatient visit (moderate exacerbation) as the primary diagnosis. Multiple exacerbations occurring within 14 days of each other will be considered as a single exacerbation and will be per the higher severity. A schematic of the study design is presented below in Figure 1.

Boehringer Ingelheim Non-Interventional Study (NIS) Protocol BI Study Number 1237-0121

c38026921-01

Proprietary confidential information © 2022 Boehringer Ingelheim International GmbH or one or more of its affiliated companies

Figure 1 Study Design

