9.3 VARIABLES

The definitions for exacerbations are as below.

- A severe exacerbation will be defined as follows:
 - An inpatient admission or an ER visit with a COPD diagnosis code in the primary position; or
 - An inpatient admission or an ER visit with a diagnosis code for acute respiratory failure in the primary position and a COPD diagnosis code in any position; or
 - An inpatient admission or an ER visit with a diagnosis code for acute respiratory failure in the primary position + an inpatient admission or an ER visit within ±7 days with a COPD diagnosis code in any position.
- A moderate exacerbation will be defined as follows:
 - An ambulatory (office or outpatient) visits with a COPD diagnosis code in any position + a pharmacy claim for an oral corticosteroid (OCS) prescription within ±7 days of the office/outpatient visit; or

Proprietary confidential information © 2022 Boehringer Ingelheim International GmbH or one or more of its affiliated companies

- \circ An office or outpatient visit with a COPD diagnosis code in any position + a pharmacy claim for respiratory antibiotic prescription within ±7 days of the office/outpatient visit; or
- An office or outpatient visit with a COPD diagnosis code in any position + a pharmacy claim for an OCS + a pharmacy claim for respiratory antibiotic prescription within ±7 days of the office/outpatient visit.
- Pneumonia diagnosis: Binary indicators will be created to identify patients with a diagnosis of 1) pneumonia (Appendix 1). The time to first pneumonia diagnosis, and time to first pneumonia, during follow-up will also be captured.
- Pneumonia-related hospitalization: Binary indicators will be created to identify
 patients with an acute hospitalization with diagnosis of 1) pneumonia in any
 position (Appendix 1) The time to first pneumonia-related hospitalization during
 follow-up will also be captured.
- COPD exacerbation and/or pneumonia diagnosis: Binary indicators will be created to identify patients with each of the following composite outcomes: severe COPD exacerbation or an acute hospitalization with a diagnosis of pneumonia in any position, severe COPD exacerbation or a hospitalization with a diagnosis of pneumonia in any position, any COPD exacerbation or pneumonia diagnosis in any position, and any COPD exacerbation or pneumonia diagnosis in any position. Time to event variables will be created for each composite outcome during the follow-up period.

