APPENDIX 3: COPD GUIDELINE-RECOMMEND ANTIBIOTIC MEDICATIONS

Drug Category	Drug Class	Medication	
COPD Guideline-		cefaclor	
recommended Antibiotics ¹		cefdinir	
		cefditoren	
		cefepime	
	Cephalosporins	cefpodoxime	
		cefprozil	
		ceftibuten	
		ceftriaxone	
		cefuroxime	
	M	azithromycin	
	Wacrondes	clarithromycin	
		amoxicillin	
	Penicillins	amoxicillin/potassium	
		piperacillin/tazobactam	
		levofloxacin	
	Quinoiones	moxifloxacin	
	Sulfonamide	sulfamethoxazole/trimethoprim	
	combinations		
	Tetracyclines	doxycycline	

¹The American Thoracic Society (2017) and Global Initiative for Chronic Obstructive Lung Disease (2020) guidelines recommend that antibiotics for acute exacerbation of chronic bronchitis be selected based on local sensitivity patterns. For more specific recommendations, The Sanford Guide to Antimicrobial Therapy (2020) was referenced.

COPD Exacerbation Definition

- **Exacerbation Hierarchy:** Exacerbation events will be classified as severe or moderate according to the highest severity contributing event.
- **Exacerbation Episodes:** Exacerbations occurring within 14 days of each other will be considered a single exacerbation episode and will be classified according to the highest severity contributing event.
- Episode Length: The start date of the exacerbation episode will be the service date of the first event (medical encounter or pharmacy fill for an OCS or antibiotic). The end date of the exacerbation episode will be defined as the last observed exacerbation event date (or discharge date if an inpatient event) + 14 days.

Proprietary confidential information © 2022 Boehringer Ingelheim International GmbH or one or more of its affiliated companies

• Single Event Episode

- In a single event episode, the exacerbation begins with the earliest occurrence of these events: COPD exacerbation defined inpatient admission, ER visit, ambulatory visit, or corticosteroid or antibiotic dispensing as defined in Section 9.3.2.1. In a single event episode, the exacerbation ends 14 days from the start of the event, hospital discharge, or following the OCS or antibiotic dispensing, whichever is later.
- *Episode Start date* = service date of a qualifying event (inpatient admission, ED visit, ambulatory visit, or OCS or antibiotic dispensing).
 - If the qualifying event is a hospitalization, the start date is the admission date.
 - If the qualifying event is an ED visit, the start date is the service date.

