 - If the qualifying event is an ambulatory visit or an OCS or antibiotic dispensing, the start date is the earliest of the associated medical visit or medication dispensing date.

Episode End Date

- \circ If the qualifying event is a hospitalization: discharge date + 14 days
- \circ If the qualifying event is an ER visit: start date + 14 days
- If the qualifying event is an ambulatory visit or an OCS or antibiotic dispensing: Fthe latest of the medical visit or medication dispensing + 14 days
- If the Episode End Date is after the end of follow-up, then set an additional flag CENSORED=1.
- NOTE: Under this definition, it is possible for the runout of a medication to exceed the End Date.
- MULTIPLE EVENT EPISODES
- If another qualifying event occurs before the episode End Date, then the episode is extended. The date of the second event is used to reset the End Date per the definition above, using information from this second event. The process continues until a 14-day period with no exacerbation qualifying events occur. The End Date is set (as defined above).
- *Episode Length:* (End date Start date) + 1

Proprietary confidential information © 2022 Boehringer Ingelheim International GmbH or one or more of its affiliated companies

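### Moderate exacerbations, part of the primary endpoint, are defined in three incompatible ways, and the plan does not say which definition prevails

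*Combined protocol and SAP*

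**What the plan says.** Moderate events are described in three places.

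- **Section 9.3.2.1 (Primary Outcomes)** counts "An antibiotic for a respiratory condition dispensed", with or without an OCS. Its timing sentence adds "on the same day (moderate exacerbation". No visit, no COPD code and no OCS-only route is mentioned.
- **Section 9.3 (Variables)** lists three routes, all tied to an office or outpatient visit with COPD coded anywhere on the claim. The first is "An ambulatory (office or outpatient) visits with a COPD diagnosis code in any position + a pharmacy claim for an oral corticosteroid (OCS) prescription", the two no more than 7 days apart. The other two replace the OCS with a respiratory antibiotic, or require both.
- **The abstract and Sections 9.1 and 9.2.2** take a respiratory antibiotic, with or without an OCS, within 7 days of an "office/outpatient visit (moderate exacerbation) as the primary diagnosis". An OCS alone does not qualify.

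Severe events differ too. Section 9.3 needs COPD as the primary code for an emergency department (ED) visit. Section 9.3.2.1 asks for "An emergency department (ED) visit with a discharge diagnosis of COPD" and gives no code position. Section 9.3 also has a respiratory-failure route built from two separate encounters ("primary position + an inpatient admission or an ER visit within", the limit being 7 days), which Section 9.3.2.1 lacks.

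Appendix 3 sets the episode rules. It refers to an "ambulatory visit, or corticosteroid or antibiotic dispensing as defined in Section 9.3.2.1", and for visit or dispensing events "the start date is the earliest of the associated medical visit or medication dispensing date".

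**The concern.** Sections 9.3 and 9.3.2.1 each present their text as the definition of the event, and no sentence ranks one above the other. Section 9.3.2.1 combines moderate and severe events for the main analysis, so the moderate definition feeds the primary Cox model and the exacerbation counts directly.

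Read literally, the primary-outcome section misses COPD visits treated with an OCS alone. It can also count antibiotic fills with no COPD-coded encounter. It does not say how a fill is judged to be for a respiratory condition, and Section 9.9 concedes that indication can only be inferred from diagnostic patterns.

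Two competent programmers could produce different primary hazard ratios, each defensible from the protocol. Because the claims already exist, a definition left open could be settled after results are visible.

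**Working it through.** The plan states no figure for this point, so the check sets the definitions side by side. The claims patterns below are illustrative and say nothing about frequency.

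| Claims pattern | Section 9.3.2.1 | Section 9.3 | Abstract, 9.1, 9.2.2 |
|---|---|---|---|
| COPD-coded office visit, OCS only within 7 days | no event | moderate | no event |
| Antibiotic fill, no visit within 7 days | open: depends how respiratory use is established | no event | no event |
| Office visit with COPD as a secondary code, antibiotic within 7 days | moderate if the fill is judged respiratory | moderate | no event if the primary-diagnosis phrase governs the visit |
| ED visit, COPD secondary, no respiratory failure | open: position unstated | not severe | unclear |
| Admission with respiratory failure primary and no COPD code, then a second within 7 days with COPD non-primary | no event | severe | route not mentioned |
| Admission with COPD primary | severe | severe | severe |

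**Nesting.** The first row is in the Section 9.3 set but not the 9.3.2.1 set. The second row can be in the 9.3.2.1 set but not the 9.3 set. The two overlap and neither contains the other.

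**Pointer.** Appendix 3 relies on Section 9.3.2.1 for ambulatory-visit and corticosteroid events. Section 9.3.2.1 defines neither, and the OCS-only route appears only in Section 9.3.

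**Event date.** Take Section 9.3's third route, with the visit on day v, the OCS on day v − 7 and the antibiotic on day v + 7.

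- Appendix 3 start: min(v − 7, v, v + 7) = v − 7.
- Section 9.3.2.1 date, measured to the antibiotic: v + 7.
- Difference: (v + 7) − (v − 7) = 14 days within one event.

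This comparison assumes that the Appendix 3 episode start serves as the Cox event date. The plan does not say whether it does.

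**Follow-up boundary.** Section 9.3.1 places the index date in baseline and assesses outcomes from index date +1. With a visit on day 0 and an antibiotic on day +7, the Appendix 3 date is day 0 (baseline) and the Section 9.3.2.1 date is day +7 (a primary event). A visit before and a fill after the 12-month limit, or any earlier censoring date, gives the reverse.

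**Baseline history (linked, secondary).** Section 9.7.1 places ED visits among outpatient events, the group it equates with moderate exacerbations in the low-history stratum. Sections 9.3 and 9.3.2.1 make a qualifying COPD ED visit severe. A patient whose only baseline event is one such visit has 0 inpatient and 1 outpatient event and so falls in the low-history stratum, although the same visit in follow-up would be severe. Section 9.3.3 labels its severe history covariate by hospitalizations only.

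**The case against.** The strongest defence is that Section 9.3.2.1 is shorthand for Section 9.3. Section 9.3 introduces its list as the definitions, Appendix 3's visit and dispensing events match it, and an indication-based antibiotic trigger cannot be run from pharmacy claims alone. Sections 9.1 and 9.2.2 and the abstract are condensed design text. This makes Section 9.3 the likely intent. It does not remove the conflict: Section 9.3.2.1 says that it defines the event, sets its own same-day rule and omits OCS alone, and Appendix 3 cites it by number.

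Some mitigation stands. Severity-stratified sensitivity analyses and separate moderate and severe counts are planned, so severe-only results do not depend on the moderate definition. Index-date claims are assigned to baseline, except those for the index medication. Under the earliest-date rule that settles a visit on or before index with a later fill, but only if that rule dates the event.

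A reader might infer that the antibiotic-only definition biases the hazard ratio, because Section 7 reports a 53% greater pneumonia risk with triple therapy and pneumonia is treated with antibiotics. The documents do not support that. The 53% is background literature, and there is no split of events by type or arm. It is a reason not to assume equal misclassification, and no more. Nor can a reader conclude that any one definition leaves the study underpowered: Section 9.5 gives no significance level, target hazard ratio or event rate for its power statement.

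**Conclusion.** The conflict is real and should be resolved before programming. The moderate component of the primary endpoint has three incompatible definitions with no order of precedence. The Appendix 3 cross-reference does not fit the section it cites. The severe component differs on ED code position and on one respiratory-failure route. The Cox event date is unspecified, with up to 14 days between the two rules within one event under the assumption stated above. Confidence in these textual findings is high.

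The number of patients affected, and the size and direction of any change in the hazard ratio, cannot be derived from the documents. The primary-diagnosis phrase in Sections 9.1 and 9.2.2 is itself ambiguous: it may govern the outpatient visit or the whole sentence. The conflict between Sections 9.3 and 9.3.2.1 stands either way.

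**What to change.** Before programming, reconcile the abstract, Sections 9.1, 9.2.2, 9.3 and 9.3.2.1, and Appendix 3 to one claims algorithm, and state that it prevails. It should fix:

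- whether a COPD-coded visit is required, and the code position;
- whether an OCS alone qualifies;
- the window between visit and dispensing;
- the ED code position and the respiratory-failure routes;
- one event date for the Cox model, with a statement that a visit on or before the index date with a later fill is assigned by that date.

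Section 9.3 is the natural candidate because it is the fullest and fits Appendix 3's episode rules, subject to the sponsor confirming intent. Any antibiotic-dispensing-only version should be a named sensitivity analysis. Apply the same severity rule for ED visits in the Section 9.7.1 history strata and the Section 9.3.3 covariates.

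The cost is wording and programming on the same claims. The event count will change by an amount and in a direction not known in advance. If the baseline history variable changes, matching must be re-run and the 3018 per group in Section 9.5 may shift. The Section 9.3 version would still count an outpatient pneumonia visit that also carries a COPD code and is treated with an antibiotic, so it reduces that overlap without removing it.

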9.3.2.2 Secondary Outcome(s)

The secondary outcome is time to first hospitalization for community-acquired pneumonia (serious pneumonia). Pneumonia was defined using ICD-9-CM diagnoses 481.x-486.x; 487.0, 507.x, 507.0, 507.1, 507.8, 510.0, 510.9, 511.0, 513.0, 514.x, 517.1, 519.8, 530.84, and ICD-10 diagnosis codes J10.0; J11.0; J12-J18; J22; J69; J85.0; J85.1; J86. This definition has been previously used in COPD. ^{27,28}

- COPD and/or pneumonia related HCRU (including acute inpatient stays and their length of stay, emergency department visits, ambulatory [Physician office visits, hospital outpatient visits], and other medical visits)
- COPD-related HCRU
- Pneumonia-related HCRU
- COPD-attributable HCRU
- All-cause HCRU

HCRU is defined as total inpatient, emergency department, and outpatient care episodes. Estimates will be presented both overall and for COPD and/or pneumonia-related care, defined as claims where a diagnosis of COPD or pneumonia is present. Medications used, defined as total number of distinct medication subclasses dispensed (e.g., 4-digit level of the Generic Product Identifier) and total number of dispensing for medications per year. COPDrelated medication utilization included all COPD medications, OCS, and guidelinerecommended antibiotics

Annual HCRU costs (including costs paid by the patient, health plan, and any third party via coordination of benefits) will be then calculated as total costs, medical costs, pharmacy costs, ambulatory costs, ED costs, inpatient costs, and other costs. Costs were defined as related to COPD if the claim has a diagnosis for COPD in any position or is a pharmacy claim for a medication used to treat COPD. The sum of all costs from all care settings and pharmacy dispensing will be assessed overall, for COPD and/or pneumonia-related care.

9.3.3 Covariates

Patient characteristics at baseline will be assessed for Stiolto and Trelegy users overall and stratified by history of exacerbation.

The covariates included in the Propensity Score Matching (PSM) will include all the below covariates including the ones defined during the 12-month pre-index baseline period and chronic comorbid conditions.

- Gender
- Age group (years, categorical and a continuous variable)
- Calendar year of cohort entry
- Region
- Insurance type (e.g., Commercial, Medicare)
- Season of index date (winter, spring, summer, fall)

Additional characteristics that will be defined during the 12-month pre-index baseline period:

- Previous acute COPD exacerbation (measured both overall and in the 30 days prior to cohort entry), categorized as 0, 1, or ≥2.
 - All exacerbations (Moderate+Severe)
 - Hospitalizations (Severe)
- Use of other respiratory drugs in the 12-month pre-index period:
 - Short-acting beta-agonists
 - Short-acting Anticholinergics
 - Methylxanthines
 - o LAMA
 - o LABA

Proprietary confidential information © 2022 Boehringer Ingelheim International GmbH or one or more of its affiliated companies

- o ICS
- o ICS/LABA
- Use of antibiotics commonly prescribed for a respiratory condition (e.g., azithromycin)
- Use of OCS
- Oxygen Use
- Pulmonary Rehabilitation

Chronic comorbidities were defined using diagnoses identified during all available data prior to the index date, and included

- Quan-Charlson Comorbidity Index score/individual comorbidities
- Cardiovascular disease
- Diabetes
- Renal failure
- GERD
- Arthritis
- Osteoporosis
- Cancer (excluding basal cell carcinoma)
- Baseline pneumonia diagnosis
- Baseline acute bronchitis diagnosis
- Diagnosis of dyspnea during baseline identified using ICD 9 786.0x and ICD 10 R06.0x
- Diagnosis of obesity during baseline identified using ICD 9 278.xx and ICD 10 E66.xx
- Diagnosis of alcohol dependence during baseline identified using ICD 9 303.xx, 305.0x and ICD 10 F10.xx
- Smoking dependence during baseline identified using ICD 9 305.1 and ICD 10 F17.xx
- Tobacco use or cessation counselling*

*We anticipate limited capture of lifestyle variables known to be risk factors and potential confounders, including obesity, smoking status, and excessive alcohol consumption.

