7. RATIONALE AND BACKGROUND

Chronic obstructive pulmonary disease (COPD) is a leading cause of morbidity and mortality throughout the world.¹ COPD has risen to become the third leading cause of death in the United States (US). ^{2,3} The Global Initiative for Chronic Obstructive Lung Disease (GOLD) 2020 report and the American Thoracic Society 2020 report recommends dual bronchodilator therapy (DBT) with long-acting muscarinic antagonists (LAMAs) plus long-acting beta2-agonists (LABAs) for patients with COPD who have persistent symptoms and/or exacerbations on LAMA or LABA monotherapy. ^{4,5} Consideration of escalation to triple therapy (TT; LAMA+LABA+inhaled corticosteroids [ICS]) is recommended in case of further exacerbation (\geq 2 moderate exacerbations or 1 severe exacerbation) and after assessing the risks/benefits. An important consideration is the trade-off between preventing exacerbations to restrict TT use further, to only patients who are likely to respond to ICS (such as \geq 2 moderate exacerbations or 1 severe exacerbation in the previous year, to those with asthma-COPD overlap or elevated blood eosinophils. ⁷

Page 17 of 47

c38026921-01

Proprietary confidential information © 2022 Boehringer Ingelheim International GmbH or one or more of its affiliated companies

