9.7.1 Main analysis

Analyses will be presented comparing Stiolto vs Trelegy overall after PSM matching and stratified as follows if the sample size allows (at least 15% in each strata):

• Low history of exacerbation: 0 inpatient (i.e., severe exacerbations) and 0-1 outpatient events (i.e., moderate exacerbations)

Proprietary confidential information © 2022 Boehringer Ingelheim International GmbH or one or more of its affiliated companies

• High history of exacerbation: ≥1 inpatient (i.e., severe exacerbations) or ≥2 outpatient events (includes ED)

We will describe the formation of the study cohort. Patient characteristics at baseline in patients treated with Stiolto and patients treated with Trelegy will be assessed separately using standard descriptive statistics.

Propensity scores including both pre-specified and data-derived variables will be then calculated. Balance of patient characteristics between the cohorts will be described before and after propensity score application and compared using standardized differences. For each Stiolto patient, a Trelegy patient with the closest available propensity score will be selected. Nearest neighbor matching method with a caliper of 0.2 will be utilized. Standardized differences greater than 0.10 (10%) will be taken to indicate imbalance, and these variables will also be included in outcome models, categorized as appropriate.

For the analysis of the primary objective, a Cox proportional hazard regression model will be used to perform an as-treated analysis that assesses the effect of first line maintenance medication with Stiolto versus the first line maintenance medication with Trelegy on the time to first COPD exacerbation. This estimates the HR of a COPD exacerbation associated with Stiolto use relative to Trelegy use, along with 95% CI. Based on the days' supply post index date, allowing a grace period of 45 days following the end of days' supply to account for intermittent use.

Stratified analyses will be using the same approach as the main analysis. Calculation of propensity scores will be repeated within the subset of the cohort with available results to create weighted populations suitable for these stratified analyses.

The analysis of the secondary objective related to the risk of pneumonia will also be assessed using Cox proportional hazard regression models with an as-treated approach, like that of the primary analysis.

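### Prior exacerbations are top-coded at two or more in the propensity score, so balance on the number of events among frequent exacerbators is neither ensured nor directly checked

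*Combined protocol and SAP*

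**What the plan says.** Section 9.3.3 lists the propensity-score covariates. Exacerbation history in the 12-month baseline is entered as "Previous acute COPD exacerbation (measured both overall and in the 30 days prior to cohort entry), categorized as 0, 1, or ≥2". Two such variables are listed, one for all exacerbations (moderate plus severe) and one for severe exacerbations (hospitalizations). The same list holds oral corticosteroid (OCS) use, respiratory antibiotics, oxygen and short-acting drugs, without saying whether these are yes/no or counts. Age, by contrast, is entered both in categories and as a continuous variable.

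Section 9.7.1 allows further, unnamed variables: "Propensity scores including both pre-specified and data-derived variables will be then calculated". It defines the upper stratum as "High history of exacerbation: ≥1 inpatient (i.e., severe exacerbations) or ≥2 outpatient events (includes ED"), and says of the stratified analyses: "Calculation of propensity scores will be repeated within the subset of the cohort with available results". Strata are analysed only if each holds at least 15% of patients.

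Sections 9.2.4, 9.7 and 9.7.1 judge balance by a standardized difference of 0.10. A larger value leads to covariate adjustment, interaction terms to match on, or discontinuation.

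**The concern.** Prior exacerbations are the same kind of event as the primary outcome, and section 9.9 says that lung function and symptom scores will not be available. The exacerbation history is therefore one of the few direct severity measures left. With an open top category, matching can equalise the share of patients with ≥2 events while one cohort still has more events per patient within that category. The balance check, applied to the same categories, would pass.

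The High-history stratum is most exposed, because most of its patients fall in the open category. If Trelegy starters there had more prior events, they would also be expected to have earlier exacerbations, and the hazard ratio would favour Stiolto for a reason unrelated to the drugs.

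**Working it through.** The documents give no distribution of prior exacerbations and no figure on this point to reproduce. The logic comes from the text. The sizes rest on assumptions stated at each step.

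**Step 1: levels possible in the High-history stratum.** Entry needs ≥1 inpatient event or ≥2 outpatient events. The all-exacerbations variable therefore cannot be 0, and it is 1 only when the single event was an inpatient one. Everyone else is ≥2. The severe variable can still be 0, 1 or ≥2.

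**Step 2: gap left inside ≥2 after perfect balance on 0/1/≥2.** Assumptions: negative-binomial yearly counts with mean 0.5 vs 0.7, or 0.6 vs 0.9 (Stiolto vs Trelegy); size parameter *k* of 0.5 or 1; no drug effect; hazard multiplied by *h* = 1.10 to 1.20 per prior event; no help from other covariates.

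Worked case, *k* = 1, means 0.5 and 0.7. Given ≥2, the mean count is 2 + mean and the variance is mean × (1 + mean).
- Mean counts are 2.50 and 2.70, so the standardized difference is 0.20 / √((0.75 + 1.19)/2) = 0.20.
- The mean relative hazard is h²p / (1 − (1 − p)h), with p = 1/(1 + mean). At h = 1.20 this gives 1.44 × 0.6667 / 0.6000 = 1.600 and 1.44 × 0.5882 / 0.5059 = 1.674.
- The ratio is 1.674 / 1.600 = 1.047.

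The overall ratio is (p0 + p1·h + p2·E_T) / (p0 + p1·h + p2·E_S). Here p0, p1 and p2 are Stiolto's shares with 0, 1 and ≥2 events, because Trelegy patients are matched to Stiolto patients. E_T and E_S are the mean relative hazards within ≥2. For the largest case: (0.674 + 0.221 + 0.142 × 2.006) / (0.674 + 0.221 + 0.142 × 1.777) = 1.028.

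| Means | k | Share ≥2, S / T | Mean count in ≥2, S / T | Std. diff. in ≥2 | T/S ratio in ≥2, h = 1.10 to 1.20 | T/S ratio overall |
|---|---|---|---|---|---|---|
| 0.5 vs 0.7 | 0.5 | 0.116 / 0.166 | 2.78 / 3.08 | 0.21 | 1.034 to 1.079 | 1.005 to 1.014 |
| 0.5 vs 0.7 | 1 | 0.111 / 0.170 | 2.50 / 2.70 | 0.20 | 1.022 to 1.047 | 1.003 to 1.007 |
| 0.6 vs 0.9 | 0.5 | 0.142 / 0.210 | 2.93 / 3.37 | 0.26 | 1.052 to 1.129 | 1.009 to 1.028 |
| 0.6 vs 0.9 | 1 | 0.141 / 0.224 | 2.60 / 2.90 | 0.26 | 1.033 to 1.073 | 1.006 to 1.015 |

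With Trelegy's shares instead, the largest overall value would be (0.598 + 0.231 + 0.210 × 2.006) / (0.598 + 0.231 + 0.210 × 1.777) = 1.04.

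**Step 3: with other covariates in the score.** A simulation used 3996 + 5121 = 9117 patients (section 9.5), 20 replicates and 9 scenarios. Assumed: means of 0.85 to 1.9 events per year, and log-odds of Trelegy of 0.1 to 0.3 per moderate event, doubled per severe event. The score held both exacerbation variables in the plan's coding (12 months and 30 days) plus yes/no OCS and antibiotic use. Matching was 1:1 nearest neighbour with a caliper of 0.2, taken as standard deviations of the logit because the plan gives no scale.

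| Absolute standardized difference | Before matching | Plan's coding | Counts added |
|---|---|---|---|
| ≥2 indicator | not tabulated | ≤0.005 | ≤0.008 |
| Count, whole cohort | 0.15–0.64 | 0.02–0.14 | ≤0.006 |
| Count, patients with ≥2 | 0.16–0.62 | 0.11–0.39 | ≤0.014 |
| Count, refitted High stratum | 0.16–0.61 | 0.07–0.31 | ≤0.007 |

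- The High stratum was 24–48% of patients. Of these, 84–90% were ≥2 on all exacerbations, while severe was 0 in 37–48%, 1 in 43–46% and ≥2 in 8–17%.
- The plan's coding removed 23–41% of the raw count imbalance among ≥2 patients (for example 1 − 0.388/0.615 = 37%) and 45–55% in the High stratum (1 − 0.307/0.610 = 50%).
- The count still exceeded 0.10 in 8 of 9 scenarios in the High stratum, but in only 2 of 9 in the whole cohort.
- The remaining gap in High was 0.11 to 0.56 events, more in Trelegy. As a ratio this is 1.10^0.11 = 1.01 to 1.20^0.56 = 1.11.

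**The case against.** The strongest reply is that the cut-points follow the criterion cited in section 7 for escalating to triple therapy (two moderate events or one severe), so the threshold is represented, and finer steps above it are a choice of functional form. That stands as a defence of the threshold. It does not cover choice that depends on the count above it.

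A reader might infer more than the documents support:

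- **That exacerbation count is the main channeling factor.** Section 7 reports guideline criteria. On actual first-line use in naïve patients it points instead to convenience and says the practice runs against guidelines. No text says that choice depends on the count.
- **That the count cannot be balanced, or that history hardly varies in the High stratum.** The severe variable varies there, and the listed covariates removed part of the gap in Step 3. Balance is not ensured, which is a weaker statement.
- **That the balance check cannot detect the gap.** Section 9.3 also measures baseline visit and inpatient counts and the number of fills by drug class, OCS among them. Section 9.7 applies the 0.10 rule to any baseline characteristic. The plan does not say that these counts enter the balance table, but they could reveal the gap indirectly.
- **That the High stratum is where triple therapy is known to help.** The hazard ratio of 0.83 in section 9.5 is for two or more prior exacerbations. The High stratum also admits a single inpatient event.

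The stratified analysis also depends on the 15% rule. Under the Step 2 assumptions only 11–14% of Stiolto patients have ≥2 events, though single inpatient events enlarge the stratum. Sections 9.7 and 9.9 allow sensitivity and bias analyses but name none on this variable.

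**Conclusion.** The point holds in a limited form. The plan fixes an open top category for exacerbation history and pre-specifies no count, in the score or in the balance check. If Trelegy is given preferentially to patients with more prior events, the matched comparison would lean toward Stiolto.

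Under no true drug effect, the spurious Trelegy/Stiolto ratio is about 1.01 to 1.13 in ≥2 or High-history patients. On the plan's Stiolto/Trelegy scale the hazard ratio would be about 1% to 11% too low (1/1.01 = 0.99; 1/1.13 = 0.88). Overall the ratio is about 1.003 to 1.03 with Stiolto's case mix, so this is mainly an issue for the High-history results and not a reason to doubt the primary comparison by itself. The Step 2 values allow for no other covariates and are upper values for their inputs. Count distribution, channeling strength and hazard per event are all assumed, and the documents supply none of them.

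**What to change.** In section 9.3.3, keep 0/1/≥2 and also enter prior moderate and prior severe exacerbations as counts, either capped or with finer upper categories (for example 0, 1, 2, 3, ≥4), in the overall and the stratum-specific propensity models. This follows the plan's own handling of age. In sections 9.2.4 and 9.7, name these counts in the standardized-difference check, reported overall and within the High-history stratum.

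No new data are needed, since the episode rules that follow Appendix 3 already yield countable events. The cost is a few more model terms and possibly slightly fewer pairs. In the simulation, the largest fall in mean matched pairs was from 3,756 to 3,745 overall (0.3%) and from 1,329 to 1,321 in the High stratum (0.6%).
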